BACKGROUND	
Renal denervation (RDN) is a recent procedure that can be used to control BP (blood pressure) in hypertensive patients. Numerous publications from randomised trials have demonstrated the efficacy of RDN in this indication (1-14). The latest guidelines now include RDN as an effective technique for use in hypertension. Since the beginning of 2023, RDN using Medtronic's Spiral radiofrequency system has benefited from transitional authorisation for reimbursement by the French health insurance system. An application for reimbursement is underway for the ultrasound system.
 
We aim to compile an exhaustive prospective register of all procedures carried out in France over the next few years, regardless of the type of catheter used or the context in which the procedure was carried out (transitional reimbursement, industrial register, randomised trial). Our aim is to assess the efficacy and safety of the procedure within the French healthcare system, the characteristics of patients benefiting from the procedure, the centres performing renal denervation, and the care pathways used, and to be able to present all this data, independently of the industry, to the healthcare authorities when it comes time to reassess the value of this procedure and its indications.

PRIMARY OBJECTIVE	 Diagnostics  Prevention and treatment  Patient management  Patient safety  Organization of healthcare facilities  Public health policies  Understanding diseases  Other: To describe changes in SBP evaluated in Home Blood Pressure Measurement (HBPM) in hypertensive patients between before and 1 year after treatment with RDN.
PRIMARY ENDPOINT	Change in SBP measured by HBPM before and after RDN (1 year).

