SECONDARY OBJECTIVES	SECONDARY OBJECTIVES: - To evaluate changes in office systolic blood pressure, the combination of SBP measured in HBPM and day ABPM and 24-hour SBP before and 3 months, 6 months, 1 year, after DNR. - Evaluate the evolution at 3 months, 6 months, 1 year, of the drug burden in antihypertensive treatment (DDD), the percentage of patients having reached the blood pressure target and the win ratio. - Evaluate the development of renal artery stenosis before and 6 months, 1 year, after DNR. - Evaluate the evolution of creatinine levels before and 6 months, 1 year, after DNR. - Evaluate the occurrence of other complications related to hypertension or to the procedure itself. - Comparison of responders and non-responders to the procedure (24h ABPM systolic blood pressure decrease of 5 mmHg or more and/or the diminution of the medical burden by at least one therapeutic class without SBP increase compared to baseline). - Evaluate the performance of known predictors of response to renal denervation in our population. - Describe the type of center performing the procedure, the context in which DNR is performed, patient characteristics and care pathways.
METHODOLOGY	Research that does not involve the human person, as it involves the prospective, retrospective, descriptive and comparative use of multicentric data from routine care.
TYPE OF DATA COLLECTED	The data collected are detailed below: 
 • Administrative data : - centre number followed by a hyphen (-) then the patient's number - collection of the patient's non-objection to participate in the FRiEND register - date of inclusion, date of procedure

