	
 - type of centre carrying out the procedure (hospital, university hospital, clinic, ESPIC, other) - setting in which the procedure was carried out (day hospitalisation, week hospitalisation, conventional hospitalisation) 
• Personal data :
 
 - Patient's initials, date of birth (in MM/YYYY format). - Gender (male, female, not gendered, refuses to answer), height, weight, 
• Biological data :
 
 - Biological work-up with measurement of the following parameters: Plasma ionogram (Na, K), blood count and platelet count (NFP), proteinuria, fasting glycaemia, total cholesterol, LDL cholesterol, HDL cholesterol, triglycerides, creatininaemia, estimated glomerular filtration rate (eDFG) (according to the Modification of Diet in Renal Disease (MDRD) method), uricaemia, microalbuminuria or urinary albumin/creatinine (assessment of target organ damage). 
• Clinical data :
 
 - Systolic blood pressure (SBP), diastolic blood pressure (DBP), heart rate (HR): three measurements will be taken with a validated oscillometric electronic device measured according to international recommendations (2023ESH-ESC) - risk factors (dyslipidaemia, type 2 diabetes, hypertension, smoking) - cardiovascular (CV) history of more than 6 months (myocardial infarction, coronary insufficiency, stroke) - non-CV history (cancer, asthma or respiratory insufficiency, musculoskeletal disability) - ABPM measurement (SBP and DBP for 24 hours, during the day and at night) - self-measurement of BP (according to the rule of 3 : average of 3 measurements in the morning and 3 in the evening, 3 consecutive days). - current treatments (anti-hypertensive, lipid-lowering, anti-diabetic, anti-platelet). - Therapeutic adherence assessment 
• Imaging data :
 
 - results of CT scan of renal arteries: number of renal arteries, diameter of renal arteries, assessment of possible renal artery stenosis (in %) - Renal artery echodoppler (if feasible): assessment of possible renal artery stenosis (in %), renal artery blood flow velocity.
--	---

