	
Statistical analysis: Absolute values, percentages and means (SD) will be calculated to describe the population.
 
The differences between the variables before and after the RDN will be tested using either a paired t-test for normally distributed data or a Wilcoxon test, and a paired Chi2 or a Fisher test. For univariate analysis of variables between the RDN responder groups (5 mmHg reduction in 24h SBP) and non-responders, we will use the t-student analysis of variance test or non-parametric tests for continuous variables, and chi2 or Fisher tests for categorical variables. A multivariate analysis will also be performed.

PEOPLE INCLUDED IN THE RESEARCH	
Number of subjects: Estimation of 100 per year (might be less in the first year, then more as RDN implementation in France increase)
 
Inclusion criteria: Adult (> 18 years old) hypertensive patients treated with RDN in France whatever the catheter and the indication. This might include retrospective data for patient already treated with RDN in the past.

	
Non-inclusion criteria: RDN not proposed to the patient, patient opposing the collection and use of his/her data for research purposes.
 
Information and traceability procedures for non-objection/opposition :
 
Patients will be fully and fairly informed, in comprehensible terms, of the objectives of the study and the nature of the information collected, and of their right to object at any time to the use of the data collected. They will be given an information letter and the non opposition will be written down in the medical records of the patient. If the subject objects to their personal health data being processed for research purposes, this objection will be recorded in their medical file. This right of objection may be exercised at any time by any means with either the person responsible for the research or the establishment holding the data, which undertake to respond to the request within a maximum of 2 months.
 
Retrospective patients will be informed by post. On receipt of this letter, the patient will have 4 weeks to object.

ETHICS	NA

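### The only analysis stated for the development of renal artery stenosis is a before/after test of net change, which gives neither the proportion with a new stenosis nor its upper confidence limit

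*Protocol*

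**What the plan says.** The Background section sets out a safety purpose: "Our aim is to assess the efficacy and safety of the procedure within the French healthcare system". Two of the secondary objectives concern the renal artery and the kidney: "Evaluate the development of renal artery stenosis before and 6 months, 1 year, after DNR" and "Evaluate the evolution of creatinine levels before and 6 months, 1 year, after DNR". The next objective is "Evaluate the occurrence of other complications related to hypertension or to the procedure itself". The word *other* suggests that the two before it are also regarded as possible complications.

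The imaging data list records stenosis in per cent, on CT and, where feasible, on Doppler ultrasound. It gives no threshold that defines a new stenosis.

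The Statistical analysis paragraph has one rule for all before/after comparisons: "The differences between the variables before and after the RDN will be tested using either a paired t-test" if the data are normal, otherwise a Wilcoxon test, "and a paired Chi2 or a Fisher test". Counts, percentages and means are promised in a separate sentence, for describing the population. No incidence or confidence interval is attached to stenosis.

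**The concern.** Development of a stenosis is an event in one direction. The question is how many patients without a stenosis at baseline have one later, and how large that proportion could plausibly be. A test of net change answers a different question: whether gains and losses balance.

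Apparent regressions are plausible here. The data come from routine care, and per cent stenosis may be read by CT or by ultrasound, so the baseline and follow-up readings may come from different methods. Each stenosis that seems to disappear offsets a real new one in the test.

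The protocol says that the results are meant to inform health authorities on reimbursement and indications. Such a reader needs the proportion affected and its upper limit. A p-value for net change supplies neither.

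**Working it through.** The protocol gives no sample-size calculation, significance level, safety margin or expected stenosis rate, so there is no figure of its own to reproduce. The check compares what the stated tests return with what the objective asks for.

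**Inputs from the protocol.** About 100 patients per year, with inclusions from April 2025 to April 2027: 2 × 100 = 200 prospective patients. Retrospective patients would add to this, and missing follow-up imaging would reduce it.

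**Assumed inputs.** All 200 are imaged before and after; all stenosis counts; two-sided 5% level and 95% intervals.

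**Stated test, categorical form.** The exact McNemar test uses only the discordant pairs, b new and c apparently resolved. For b > c, p = 2 × P(X ≥ b), with X binomial(b + c, 0.5).

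- b = 6, c = 0: p = 2 × (1/64) = 0.031
- b = 6, c = 2: p = 2 × (28 + 8 + 1)/256 = 0.29
- b = 6, c = 3: p = 2 × (84 + 36 + 9 + 1)/512 = 0.51
- b = 6, c = 6: p = 1.0
- b = 5, c = 0: p = 2 × (1/32) = 0.0625

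In the first four rows the number of patients with a new stenosis is the same. Only the apparent regressions differ, and p moves from 0.03 to 1.0. A Fisher test on the before and after counts compares two prevalences, so it too reflects only the net difference.

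**What the objective asks for.** Incidence = new stenoses / patients at risk and re-imaged, with a Clopper-Pearson 95% interval.

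- 6/200 = 3.0% (1.1 to 6.4%). If the three apparent regressions are removed from the denominator because they had a stenosis at baseline, 6/197 = 3.0% (1.1 to 6.5%).
- 0/200 = 0%, upper limit 1 − 0.025^(1/200) = 1.8%.
- For other numbers imaged, the upper limit with no events is 3.6% at 100 and 1.2% at 300. With 6 events the interval is 2.2 to 12.6% at 100 and 0.7 to 4.3% at 300.

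The McNemar p-value is the same at 100, 200 or 300 patients, because concordant pairs do not enter it. It therefore does not show how many patients were imaged.

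**Stated test, continuous form.** Suppose three patients go from 0 to 60% stenosis and 197 do not change. The mean change is 180/200 = 0.9 percentage points. Such data are far from normal, so the protocol's rule leads to the Wilcoxon test. With three non-zero differences of the same sign, its exact p is 2 × (1/8) = 0.25. That result hides three marked changes.

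**Creatinine.** The objective concerns how the level evolves, and a paired mean change answers that. A mean can still mask individuals. Assume that 5% of patients rise by 60 µmol/L and the other 95% fall by 3 on average. The mean change is then 0.05 × 60 − 0.95 × 3 = +0.15 µmol/L. In simulation at 200 patients, with an assumed SD of change of 15 in the patients who do not rise, the paired t-test rejects about 1% of the time. If the others do not change on average, it rejects about 59% of the time.

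**The case against.** The strongest reply is that the Statistical analysis paragraph is one general sentence. It assigns no test to stenosis by name and does not rule out further summaries. Thresholds, denominators and interval methods are commonly left to a statistical analysis plan, which may exist. The number of new stenoses is also one cell of the paired table, so it need not be lost. Part of this stands: the absence of a threshold or interval method in a protocol is not an error in itself. What remains is that the protocol does state a method for before/after variables, and that method does not match an objective worded as development of stenosis.

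A second reply is that cancellation needs apparent regressions, and the protocol gives no rates. That also stands. With 6 new and none resolved, the exact test is significant at 5% (p = 0.031). The counts above show how the test behaves; they do not predict the result. Even without regressions, the test does not supply the incidence or its limit.

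Two stronger readings are tempting, and the document supports neither. A reader might infer that the protocol will take a non-significant test as evidence of safety. It contains no such rule, margin or claim; this is only a risk that arises when no estimate with an interval is named. A reader might also infer that the creatinine analysis is wrong. It is not, because a mean change describes the evolution of creatinine; a proportion worsening would be an addition.

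**Conclusion.** The point holds for stenosis. The stated before/after tests measure net change and do not answer an objective on new stenosis. With an assumed 200 re-imaged patients and 6 new stenoses, p ranges from 0.03 to 1.0 according to how many apparent regressions occur (0 to 6), while the incidence stays at 3.0% (95% CI 1.1 to 6.4%). With no events the upper limit is still 1.8%. The 200 follows from the protocol's accrual estimate and inclusion window; complete paired imaging and all event counts are assumptions. That stenosis is a safety outcome is inferred from the stated aim and the order of the objectives.

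For creatinine there is no error to correct, only a useful supplement. This is a worthwhile improvement to a secondary objective and does not touch the primary endpoint.

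**What to change.** In the Statistical analysis paragraph, name the stenosis analysis separately from the general before/after rule: the incidence of new stenosis above one prespecified threshold, among patients without it at baseline and with follow-up imaging, with an exact 95% confidence interval. Report beside it the number imaged out of the number treated, so that the reader can see how far routine imaging covers the cohort.

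For creatinine, keep the paired mean change. Optionally add the proportion of patients with a prespecified relative worsening of creatinine or eGFR, with an exact 95% confidence interval.

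The cost is a few sentences, the choice of one stenosis threshold before the data are examined (and a worsening criterion if the creatinine option is taken), and slightly more analysis work. No extra examinations are needed. If a statistical analysis plan already specifies these summaries, only the protocol wording needs to be brought into line.

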	 Data from the investigator's department only (coordinating and associated centers)  Data from several departments of the CHU Grenoble Alpes or from a department other than that of the investigator (if the investigator is at no time involved in the care of the persons targeted by the research).
DATA COLLECTION SCHEDULE	
Prospective and retrospective research :
 
 - 3-year register (start of collection april 2025 - end of inclusions april 2027, follow-up : 1 year) 
For retrospective patients, data collection will be done from clinical database from january 2010. A 4-week delay must be observed between the sending of information letters and the start of data collection.
 
 - End of follow-up: april 2028. - Annual analysis of data from patients who have undergone RDN and follow-up at 1 month, 6 months, 1 year after the procedure.
DATA COLLECTION	
Collection :
 
The data collected will be those from routine follow-up at 1 month, 6 months, 1 year of all patients benefiting from a RDN procedure and included in the registry. After the procedure, the investigator in each participating centre will manage the follow up of the patient. As the study is purely observational, it does not require any specific follow-up visits, but includes the collection of data obtained during routine follow-up visits. The registry does, however, include data collection at fixed times after procedure. The data reported in the Redcap file will be the data available closest to the theoretical day of collection.
 
Patients who have been lost to follow-up should be investigated through the referring doctors to RDN and/or by family members or any other person whose name appears on the patient liaison form. In the absence of any information, a search for the patient's possible death will be carried out by consulting the https://deces.matchid.io/searchqui website, including the INSEE source for deaths (the search will be carried out by birth name).
 
In case of the patient's death, the medical record is first checked to ensure that the patient has "no objection" to the use of his or her health data for research purposes.
 
Clinical data collection will be based on the source documents.

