WHY THE STUDY IS IN THE PUBLIC INTEREST	The legal basis for this data processing is Article 6 of the General Data Protection Regulation (GDPR), namely the performance of a mission of public interest assigned to the data controller and the legitimate interests pursued by it. In addition, under Article 9 of the GDPR the data controller may exceptionally process special categories of data, including health data notably for scientific research purposes.
EXPECTED BENEFITS	
To objectively evaluate RDN performance, patients and center profiles and care pathway in the various French centres participating to the registry, and to investigate whether there are any predictive factors (on the basis of the initial clinical and biological work-up) for the outcome in terms of lowering blood pressure, in order to better target patients who could benefit from this type of procedure in the future.
 
Provide informed, independent data to the health authorities to support reimbursement decisions and the choice of indications.

Study schedule

Visits	During hospitalization for RDN	1 month after RDN	6 months after RDN	12 months after RDN
Patient information	X			
RDN indication verification	X			
Blood sample	X			
Imaging examinations	X			
Medical history collection	X			
Clinical examination	X	X	X	X
Ongoing therapy collection	X	X	X	X
Adverses events recording	X	X	X	X
Blood Pressure and heart rate recording	X	X	X	X
Blood sample				
Ionogram (Na, K), glucose level, creatininemia (DFG MDRD), uricemia	X	X	X	X
Total Cholestérol, HDL, LDL triglycerides, NFP				X
Microalbuminuria, proteinuria				X
Clinical examinations				
Home Blood Pressure Measurement		X	X	X
Ambulatory Blood Pressure Measurement				X
Renal Arteries ultrasound				X
Renal arteries angioCT				X

Bibliographie :

1. Adherence to Antihypertensive Treatment and the Blood Pressure-Lowering Effects of Renal Denervation in the Renal Denervation for Hypertension (DENERHTN) Trial. Azizi M, Pereira H, Hamidouche I, Gosse P, Monge M, Bobrie G, Delsart P, Mounier-Véhier C, Courand PY, Lantelme P, Denolle T, Dourmap-Collas C, Girerd X, Michel Halimi J,

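### The primary before/after test uses only patients with both a baseline and a 1-year home SBP and ignores the 1- and 6-month readings, so loss related to response could bias the reported fall in either direction

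*Protocol*

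**What the plan says.** The Primary endpoint row of the protocol defines a two-point change: home SBP before the procedure and 1 year after it. The Statistical analysis paragraph has one sentence for all before/after comparisons of continuous variables: differences "will be tested using either a paired t-test for normally distributed data or a Wilcoxon test". It gives no separate method for the primary endpoint, and mentions neither a repeated-measures model nor a way of handling missing values.

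The Data collection row describes how readings arise: "The data collected will be those from routine follow-up at 1 month, 6 months, 1 year of all patients" in the registry. The follow-up is not imposed: "As the study is purely observational, it does not require any specific follow-up visits". Two provisions bear on missing values. The first is a closest-reading rule: "The data reported in the Redcap file will be the data available closest to the theoretical day of collection". The second is tracing: "Patients who have been lost to follow-up should be investigated through the referring doctors to RDN" or through family and other listed contacts, with a death search as the last step.

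In the Study schedule, the row "Home Blood Pressure Measurement" is marked at 1, 6 and 12 months. It has no mark in the hospitalisation column, which is the only pre-procedure column. The Type of data collected row lists self-measured BP but gives no time point for it.

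**The concern.** Both named tests work on within-patient differences. A patient without a 1-year home SBP, or without a baseline one, contributes nothing, even if 1- and 6-month readings are on file. The protocol does not use the word completers; the restriction follows from the tests.

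A complete home reading needs three morning and three evening measurements on three consecutive days. In routine care without a required visit, some patients will probably lack one at 1 year. If those patients differ in response from the rest, the mean change in the remainder is not the mean change in the registry population. The patient's 6-month reading carries information about the missing 1-year value, and the paired test discards it.

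The result is meant to inform the health authorities on reimbursement and indications, so an error of a few mmHg in the headline change matters. For scale only, the protocol's responder threshold is a 5 mmHg fall in SBP, although that is defined on 24-hour ambulatory measurement and not on home readings.

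**Working it through.** The protocol gives no SD, correlation, dropout rate or power calculation. Its figure of 100 patients per year is a volume estimate. There is therefore no stated figure to reproduce, and the size of the bias has to rest on assumptions.

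**Inputs from the protocol.** Endpoint: 1-year change in home SBP. Test: paired t-test or Wilcoxon. Home readings: 1, 6 and 12 months. Required visits: none.

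**Assumed inputs.** True mean change −8 mmHg (the bias does not depend on it). SD of change σ = 12 or 16 mmHg. Equal correlation ρ = 0.4, 0.6 or 0.8 between the 1-, 6- and 12-month changes. Missing at 12 months: 10, 20 or 30%. Logistic loss with log-odds 0, +1 or −1 per SD of change. The simulation used 200,000 patients per scenario.

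**Step 1: completers' bias when loss depends on the 6-month change.** For normally distributed changes,

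bias = ρ × σ × k,

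where k is the shift, in SD units, of the mean 6-month change among those who stay. With log-odds ±1 per SD, numerical integration gives k = 0.091, 0.173 and 0.253 at 10, 20 and 30% missing.

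| Missing | Smallest (ρ = 0.4, σ = 12) | Largest (ρ = 0.8, σ = 16) | Simulated range |
|---|---|---|---|
| 10% | 0.4 × 12 × 0.091 = 0.44 | 0.8 × 16 × 0.091 = 1.16 | 0.43 to 1.17 |
| 20% | 0.4 × 12 × 0.173 = 0.83 | 0.8 × 16 × 0.173 = 2.21 | 0.85 to 2.23 |
| 30% | 0.4 × 12 × 0.253 = 1.21 | 0.8 × 16 × 0.253 = 3.24 | 1.19 to 3.24 |

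The simulated column is for loss of poor responders, where the fall is overstated. With loss of good responders the same sizes appear with the opposite sign (for example 3.27 mmHg understated at 30%, ρ = 0.8, σ = 16). With loss unrelated to response, the bias is within 0.04 mmHg of zero.

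**Step 2: an estimate that also uses the 1- and 6-month readings.** In all of these scenarios a likelihood-type estimate is within about 0.03 mmHg of the truth. This is expected: here loss depends only on an observed value, so data are missing at random by construction.

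**Step 3: loss that depends on the unseen 12-month change.** Here k applies directly to the 12-month change, so the completers' bias is σ × k: from 12 × 0.091 = 1.09 to 16 × 0.253 = 4.05 mmHg (simulated 1.1 to 4.1). The estimate using the earlier readings is still biased by 0.3 to 3.2 mmHg. At 30% missing and σ = 16, for loss of poor responders, what remains depends on how well the earlier readings predict the last one:

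| ρ | Completers | Using 1- and 6-month readings |
|---|---|---|
| 0.4 | 4.03 | 3.20 |
| 0.6 | 4.07 | 2.39 |
| 0.8 | 4.05 | 1.30 |

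The simulation assumes complete 1- and 6-month readings. If these are missing in the same patients, the longitudinal model gains less than shown.

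**The case against.** The strongest objection is that missing-data policy belongs to a statistical analysis plan, which is not shown here. The protocol's sentence is generic, excludes neither imputation nor sensitivity analyses, and a paired comparison is a natural match for a two-point endpoint whose stated aim is descriptive. This stands in part: silence on imputation is not an error. But the protocol does name the test, and readings it already schedules support a better one, so the point concerns a stated choice.

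The protocol also has safeguards. Lost patients are traced, the reading nearest the target day is accepted, and retrospective patients enter only where the investigator believes missing data are absent or scarce. These will reduce empty 1-year fields but not abolish them. Tracing may establish vital status without yielding a home reading. The closest-reading rule has no window, so an earlier reading could stand in for 1 year. Selection of retrospective patients at entry is something no repeated-measures model can repair.

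A reader might infer that poor responders will drop out and that the published fall will therefore be too large. The protocol does not support this: it gives no dropout rate and no link between loss and response. Well-controlled patients may equally return to their usual doctor while uncontrolled ones are seen more often, and the bias would then reverse.

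**Conclusion.** The concern holds as a risk, not as a demonstrated bias. The named analysis drops patients without both home readings and leaves the 1- and 6-month readings unused, in a registry where missing 1-year values are likely. Under the assumed values, loss related to the 6-month change moves the reported fall by about 0.4 to 3.2 mmHg, overstating or understating it according to who is lost; loss unrelated to response does no harm. A repeated-measures model removes this bias when data are missing at random and only part of it when loss depends on the unseen 1-year value. Size and direction rest entirely on assumed SD, correlation, missing fraction and loss mechanism. The change is worth making because the model is no worse for bias in any of the scenarios examined beyond simulation error, and clearly better in most.

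**What to change.** - Make the primary analysis a mixed model for repeated measures with home SBP at baseline, 1, 6 and 12 months as outcomes, visit as a categorical effect, an unstructured within-patient covariance and a centre effect (for example a random intercept). Report the 12-month minus baseline mean with its 95% confidence interval, and state the missing-at-random assumption.
- Keep the paired test in completers as a sensitivity analysis.
- Add a missing-not-at-random sensitivity analysis, for example delta-adjusted.
- Report how many patients lack a 12-month home SBP, and compare baseline and 6-month SBP in those with and without it.
- Mark baseline home BP in the Study schedule, since both the paired test and the model need it. As it stands, the schedule row does not show where the pre-procedure value comes from.

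The cost is analysis wording and one schedule entry. The follow-up readings are already scheduled and the named software can fit the model. The downsides are reliance on an untestable missing-at-random assumption, only partial protection if it fails, and an estimate that may be less favourable than the completers' figure.

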	
Codage :
 
The data will be pseudonymised by coding: patients will be identified as follows: centre number followed by a hyphen (-) then the patient number coded number specific to the research indicating the order of inclusion of subjects (ex. 01-001). The list of correspondences between the patient code and his identity will be kept in each participating center, in the service server, by the investigator on an Excel file.

DATA STORAGE PERIOD	
Personal data relating to persons taking part in research, and processed for this purpose, may be kept in the information systems of the controller, the participating centre or the healthcare professional involved in the research for a maximum of 2 years after the last publication of the results of the research or, if there is no publication, until the final report of the research is signed.
 
The personal data of the professionals involved in the research may not be kept for more than fifteen years after the end of the last research project in which they participated.
 
It is then archived on paper or electronically for a period of time in accordance with the regulations in force. The data must then be deleted.

DESCRIPTION OF STATISTICAL ANALYSIS OF DATA	
NUMBER OF SUBJECTS TO BE INCLUDED
 
The number of subjects included will correspond to the number of patients undergoing renal denervation for hypertension at the Grenoble University Hospital and in the various French centres participating in the study during the study period (the estimation is currently 100 per year).
 
DATA ANALYSIS
 
The database will be stored in accordance with the signed investigator commitment, on a secure database certified to keep health data, and linked to the REDCAP system supporting the eCRF. The analyses will be carried out at the University Cardiology Clinic of the Grenoble University Hospital by [name] and [name] with the help of the SFHTA, using SPSS version 21 (SPSS Corp, Somers, NY) and STATA® 14.1 (Stata Corporation, College Station, TX).

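### Fisher's exact test, which assumes independent groups, is offered for before-after categorical comparisons in the same patients

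*Protocol*

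**What the plan says.** The protocol's section on the statistical analysis of data opens its testing plan with "The differences between the variables before and after the RDN will be tested". It then names the tests: "a paired t-test for normally distributed data or a Wilcoxon test, and a paired Chi2 or a Fisher test". The first two tests serve continuous variables and the last two categorical ones. No condition says when Fisher replaces the paired chi-square.

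The next sentence turns to responders versus non-responders and assigns "chi2 or Fisher tests for categorical variables". Those groups consist of different patients, so Fisher is appropriate there.

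Two secondary objectives could lead to a before-after test on a yes/no variable: "Evaluate the development of renal artery stenosis before and 6 months, 1 year, after DNR", and the evolution of "the percentage of patients having reached the blood pressure target". On numbers, the protocol says "the estimation is currently 100 per year". It adds retrospective patients, for whom "data collection will be done from clinical database from january 2010", without saying how many.

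**The concern.** Fisher's exact test compares proportions between independent samples. A before-after comparison has one sample with two linked readings per patient. The information about change lies in the discordant pairs, that is, patients who moved from no to yes or from yes to no. The small-sample form of the paired chi-square is the exact binomial McNemar test on those pairs, not Fisher.

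Fisher could be applied to such data in two ways, and neither is right:

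- **On the before and after counts**, it ignores the pairing. With positive within-patient correlation its standard error is too large and real changes are missed.
- **On the before-by-after cross-table**, it tests whether the two readings are associated, which is not the question. It can be highly significant when nothing has changed.

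At stake is power for secondary yes/no outcomes. It matters most for a safety signal such as new stenosis, where counts are small and an analyst is likeliest to reach for the Fisher option.

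**Working it through.** The protocol states no significance level, effect size or power for these comparisons, so there is no figure of its own to reproduce. The check is in three steps.

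**1. Why the pairing matters.** For proportions p1 (before) and p2 (after), n patients and within-patient correlation phi:

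- Variance of the difference if independent: [p1(1−p1) + p2(1−p2)] / n
- Variance if paired: [p1(1−p1) + p2(1−p2) − 2·phi·√(p1(1−p1)·p2(1−p2))] / n

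With assumed values p1 = 0.30, p2 = 0.45, n = 100 and phi = 0.5:

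- Independent: (0.2100 + 0.2475)/100 = 0.004575, standard error 0.068
- Paired: (0.4575 − 2 × 0.5 × 0.2280)/100 = 0.002295, standard error 0.048

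In 5,000 simulated data sets with these values, exact McNemar had 84% power and Fisher on the counts 55%.

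**2. Small examples (100 patients, assumed counts).**

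| Before / after | Lose / gain | Fisher on counts | Exact McNemar |
|---|---|---|---|
| 30 / 42 | 0 / 12 | 0.105 | 2 × 0.5^12 = 0.0005 |
| 30 / 42 | 15 / 27 | 0.105 | 0.088 |

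Fisher gives the same answer for both tables because it cannot see who changed. On a cross-table with 30 patients positive at each time, 5 losing and 5 gaining (no net change), Fisher returns p of about 6 × 10⁻¹⁴: it is testing association.

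**3. Power at a plausible size.** About 100 patients a year over the inclusion window (April 2025 to April 2027) gives 100 × 2 = 200 prospective patients. Event rates and correlations are assumptions. Each setting used 20,000 simulated data sets from a latent bivariate normal model, two-sided 5%. Cells show power, exact McNemar / Fisher on counts.

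| Setting | corr. 0.3 | corr. 0.5 | corr. 0.7 |
|---|---|---|---|
| n = 200, 0.5% to 4% | 57.9 / 55.8 | 60.6 / 56.1 | 64.5 / 56.0 |
| n = 200, 1% to 3% | 18.1 / 16.5 | 18.0 / 14.6 | 19.7 / 13.2 |
| n = 200, 20% to 30% | 67.8 / 60.6 | 75.6 / 62.0 | 85.0 / 62.5 |

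For 20% to 30% at correlation 0.5 and other sizes:

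- n = 100: 41.2 / 28.1
- n = 300: 90.9 / 82.8
- n = 400: 97.0 / 93.0

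There is no material loss in three situations:

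- Zero correlation (20% to 30%, n = 200): 59.0 / 59.4.
- A large effect (20% to 40%, n = 200, correlation 0.5): 99.9 / 99.8.
- An outcome absent at baseline: 0 versus 6 of 200 gives p = 0.030 with Fisher and 2 × 0.5^6 = 0.031 with exact McNemar.

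False-positive rates with no change (20% at both times, n = 200), exact McNemar / Fisher, are 3.8% / 3.7% at correlation 0, 3.5% / 1.1% at 0.5 and 3.0% / 0.5% at 0.7. Fisher on counts is conservative.

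**The case against.** The strongest counter-argument is that Fisher, when written as an alternative to chi-square, is conventionally the fallback for sparse tables. On that reading it would not be used for common outcomes. At 20% to 30% the average expected count is 25% × 200 = 50 (25 at n = 100), so the larger losses above would not occur. Simulated with Fisher used only when an expected count is below 5, power with exact McNemar throughout versus this rule at n = 200 was:

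| Setting | corr. 0.3 | corr. 0.5 | corr. 0.7 |
|---|---|---|---|
| 0.5% to 4% | 57.8 / 57.0 | 60.6 / 58.9 | 65.2 / 61.7 |
| 1% to 3% | 18.2 / 17.6 | 18.0 / 16.8 | 19.6 / 17.6 |

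The loss is then 0.6 to 3.5 points. This is a fair limit on the size, but the protocol does not state the rule, and Fisher remains the wrong test for sparse paired data.

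The wording may also be loose shorthand for an exact paired test. The same sentence leaves Wilcoxon without the word paired, although the paired version is plainly meant there. But Wilcoxon has a paired version, whereas Fisher's test is not one, and the next sentence uses Fisher in its ordinary independent-groups sense.

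Finally, no endpoint is bound to this test. Stenosis is recorded as a percentage and could be analysed as continuous. If it is dichotomised and absent at baseline, nothing is lost. The blood pressure target objective states no comparison with baseline. These points stand, and they keep the matter minor.

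**Conclusion.** The concern holds: the protocol names an independent-groups test as an option for paired categorical data. This is not a detail left to a later analysis plan, because the test is named and does not fit; an analysis plan that followed the text would carry the error forward.

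The consequence is limited. It is lost power on secondary yes/no outcomes, with no inflation of false positives as long as Fisher is run on the counts. The loss at n = 200 and correlation 0.3 to 0.7 is about 2 to 9 points for sparse events and 7 to 23 points for a change from 20% to 30% if Fisher is used freely, or under 4 points for sparse events if it is confined to small expected counts. All of these rest on assumed rates, correlations and numbers. The primary endpoint, change in home systolic pressure, is continuous and unaffected. The point is worth correcting but does not threaten the registry's main result.

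**What to change.** In the before-after sentence, replace the two categorical tests with McNemar's test, used in its exact (binomial) form when discordant pairs are few. If any before-after variable has more than two categories, name a paired method for it too. Keep Fisher only in the sentence on responders versus non-responders. The cost is one phrase in the analysis section; data collection does not change.
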